### **4.3 Withdrawal Criteria and Procedures**

In accordance with the Declaration of Helsinki (in accordance with the applicable country's acceptance), each patient is free to withdraw from the study at any time. Each investigator also has the right to withdraw a patient from the study in the event of intercurrent illness, adverse events, pregnancy (see section 7.2.4), or other reasons concerning the health or well-being of the patient, or in the case of lack of cooperation. In addition, a patient may be withdrawn from the study as described in sections 3.6, 3.8, 5.2, 5.3, and 7.1.6.

Should a patient decide to withdraw after administration of study drug, or should the investigator decide to withdraw the patient, all efforts will be made to complete and report the observations up to the time of withdrawal as thoroughly as possible. A complete final evaluation at the time of the patient's withdrawal should be made and an explanation given of why the patient is withdrawing or being withdrawn from the study.

The reason for and date of withdrawal from study drug treatment and the reason for and date of withdrawal from the study must be recorded on the CRF. If a patient withdraws consent, every attempt will be made to determine the reason. If the reason for withdrawal is an adverse event or a clinically significant abnormal laboratory test result, monitoring will continue until the event has resolved or stabilized, until the patient is referred to the care of a local health care professional, or until a determination of a cause unrelated to the study drug or study procedure is made. The specific event or test results must be recorded on the CRF. In addition, a blood sample will be obtained for measurement of the concentration of IPP-201101 from all patients who have a serious adverse event and/or have an adverse event leading to withdrawal from the study. All evaluations should be performed, according to the protocol, on the last day the patient receives study drug, or as soon as possible thereafter.

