Patients who complete the 48-week treatment period will return to the study center at week 52 for final procedures and assessments. Patients who withdraw from the study before completion of the 48-week treatment period will have their final procedures and assessments performed at their last visit. Any patient with a positive test result for anti-IPP-201101 Ab at the final study

visit will be followed with additional immunogenicity testing at 8-week intervals until the level returns to baseline value or the levels are judged by the investigator to be chronic, or the patient is lost to follow-up. Study procedures and assessments with their timing are summarized in [Table 2](#). Patients who complete all study visits will be eligible for participation in an open-label extension study to assess the continued effectiveness and safety of IPP-201101 treatment. .

The study schema is presented in [Figure 1](#).

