### **3.4 Study Drugs and Dosage**

#### **3.4.1 Investigational Product and Dosage**

IPP-201101 is a white to off-white, amorphous powder and is supplied in single-dose glass vials as lyophilized product for reconstitution. Before reconstitution, vials of study drug must be stored under refrigerated conditions (2° to 8° C [36° to 46° F]) in a secure place and protected from light. Each vial contains a sterile formulation of 220 mcg of IPP-201101, 59 mg of mannitol (and acetic acid used for pH adjustment, if necessary). This product does not contain preservatives. The study center will receive box(es) with up to 13 vials per box. Each vial will be labeled with a 4-digit treatment number and each box will contain IPP-201101. Prior to administration, IPP-201101 should be reconstituted with 1.1 mL sterile water for injection (volume of injection of 1.0 mL). After reconstitution, the vial can be stored at controlled room temperature (20° to 25° C [68° to 77° F]) for up to 2 hours prior to administration and does not need to be protected from light. Patients randomly assigned to IPP-201101 will be administered a dosage of 200 mcg sc every 4 weeks for 48 weeks (a total of 13 doses will be administered). The pharmacy manual provided by ImmuPharma or its designee includes details on storage, administration, reconstitution, syringe information, and preparation of the Investigational Product. A more detailed description of the administration procedures is given in section 5.1.

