### 3.5 Duration of Patient Participation

This study will consist of a screening period up to 2 weeks and a 48-week treatment period. Patients will return to the study center approximately 4 weeks after administration of the last dose of study drug (at 48 weeks) for the final assessment (week 52). Patients are expected to participate in the study for up to approximately 54 weeks.

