## **5 TREATMENT OF PATIENTS**

### **5.1 Study Drugs Administered**

After successfully meeting entry criteria, during the screening and baseline visits, eligible patients will be randomly assigned to the IPP-201101 treatment group or to the placebo treatment group (see section 3.3). Study drug will be packaged in single-dose vials; the study center will receive box(es) with up to 13 vials per box. Each vial will be labeled with a 4-digit treatment number and each box will contain a mix of IPP-201101 or placebo vials (see section 3.4). Study drug exposure will be measured, and study drug will be administered sc by qualified study personnel at visit 2 and visits 4 through 15. Study drug may not be administered by the same individual performing the SLEDAI-2K, BILAG-2004, or PhGA. Study drug should be administered at each study visit after all study visit procedures and assessments have been completed.

The pharmacy manual provided by ImmuPharma includes details on storage, administration, reconstitution, syringe information, and preparation of the study drug.

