### **7.1.2 Recording and Reporting Adverse Events**

For the purpose of adverse event recording, the study period is defined as that time period from signature of the informed consent form through the end of the final assessment. All adverse events that occur during the study period must be recorded on the CRF, regardless of the severity of the event or judged relationship to the study drug. For serious adverse events, the Serious Adverse Event Transmittal Form must also be completed and the serious adverse event reported immediately (see section 7.1.5). Any reported serious adverse event that occurs after the study follow-up period (regardless of time after study participation) will be assessed for its relationship to the study drug or to the patient’s participation in the study. If a serious adverse event occurs after the study follow-up period and is considered related to the study drug or a study procedure by the investigator, it must be recorded on the Serious Adverse Event Transmittal Form and reported immediately.

At each contact with the patient, the investigator must query the patient for adverse events by asking an open-ended question such as, “Have you had any unusual symptoms or medical problems since the last visit? If yes, please describe.” All reported or observed signs and symptoms will be recorded individually, except when considered manifestations of a medical condition or disease state. A precise diagnosis will be recorded whenever possible. When such a diagnosis is made, all related signs, symptoms, and any test findings will be recorded collectively as a single diagnosis on the Serious Adverse Event Transmittal Form and on the CRF.

The clinical course of each adverse event will be monitored at suitable intervals until resolved or stabilized, until the patient is referred to the care of a local health care professional, or until a determination of a cause unrelated to the study drug or study procedure is made.

The onset and end dates, duration, action taken regarding study drug, treatment administered, and outcome for each adverse event must be recorded on the CRF. The relationship of each adverse event to study drug treatment and study procedures, and the severity and seriousness of each adverse event, as judged by the investigator, must be recorded as described below.

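### Patients who withdraw have no guaranteed adverse event window after the last dose, while completers have about 4 weeks

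*Protocol*

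**What the plan says.** **Recording window.** For adverse events, section 7.1.2 of the protocol states that "the study period is defined as that time period from signature of the informed consent form through the end of the final assessment". The end of the window is therefore a visit, not a number of days after the last dose.

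**Completers.** Section 3.5 has them return "approximately 4 weeks after administration of the last dose of study drug (at 48 weeks) for the final assessment", at week 52.

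**Withdrawals.** The timing of the final assessment is stated in several ways:
- Section 3.1: patients who leave before completing treatment "will have their final procedures and assessments performed at their last visit". Section 3.11.4 and the first footnote to Table 2 say the same.
- The note to Figure 1 places it at an early termination visit.
- Section 4.3: "A complete final evaluation at the time of the patient's withdrawal should be made".
- Section 4.3, last sentence: "All evaluations should be performed, according to the protocol, on the last day the patient receives study drug, or as soon as possible thereafter".

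**Order within a visit.** Section 5.1: "Study drug should be administered at each study visit after all study visit procedures and assessments have been completed".

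**What is still captured later.** Sections 3.11.4 and 7.1.2 have ongoing adverse events followed. Sections 4.3 and 7.1.6 follow the event that led to withdrawal. Sections 7.1.2 and 7.1.5.2 keep late serious events reportable if they are judged related. Both sections mention a follow-up period, but its length is not given for patients who withdraw.

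**The concern.** The end of recording is tied to a visit whose distance from the last dose is fixed for completers and open for everyone else. An event that begins after an early final assessment is required in the database only if it is serious and judged related. New non-serious events, and serious ones judged unrelated, can be missed.

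This matters for two reasons. First, section 10.7.3 summarises adverse events as patient counts and percentages by arm, and section 10.7.1 measures treatment duration from first to last dose, so neither summary would reveal unequal observation after the last dose. If withdrawal differs between arms, so does the observed time. Second, this is a rule about data collection. Whatever the analysis plan says, it cannot recover events that were never recorded.

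**Working it through.** **1. The plan's own schedule reproduces.**
- Doses: 48/4 + 1 = 13, as section 3.4.1 states.
- Time after the last dose in completers: 52 − 48 = 4 weeks = 28 days, as section 3.5 states.
- Participation: 2 + 52 = 54 weeks, as section 3.5 states.

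**2. What each statement gives a patient who withdraws.** Let g be the days from the last dose to the final assessment.
- Last dosing day (section 4.3, last sentence, read literally): g = 0. Because assessments precede the injection, such an evaluation would in effect come before that dose.
- As soon as possible after that day, or at the time of withdrawal (section 4.3): g is whatever the timing of withdrawal makes it.
- Last visit or early termination visit (sections 3.1 and 3.11.4, Figure 1): usually between 0 and about 28 days. A patient withdrawn at the next scheduled visit, before dosing, has g = 28.

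No statement sets a lower limit on g.

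**3. Share of post-dose time unobserved.** With k doses received, 28k days would be observed if each dose had a full interval. The days observed are 28(k − 1) + g. The unobserved share is

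1 − [28(k − 1) + g]/(28k) = (28 − g)/(28k).

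At g = 0 this is 1/k, and at g = 14 it is 1/(2k).

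| Doses k | g = 0 | g = 14 | g = 28 |
|---|---|---|---|
| 1 | 100% | 50% | 0% |
| 2 | 50% | 25% | 0% |
| 3 | 33% | 17% | 0% |
| 6 | 17% | 8% | 0% |
| 12 | 8% | 4% | 0% |

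**4. Total for the trial.** The protocol gives no withdrawal rate, so 10% to 30% of the planned 200 patients is an assumption.

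| Assumed withdrawal | Patients | Lost at g = 0 | Lost at g = 14 |
|---|---|---|---|
| 10% | 20 | 20 × 28 = 560 days (1.5 patient-years) | 280 days |
| 20% | 40 | 40 × 28 = 1120 days (3.1 patient-years) | 560 days |
| 30% | 60 | 60 × 28 = 1680 days (4.6 patient-years) | 840 days |

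The g = 0 column is an upper bound, reached only if every withdrawal is assessed on a dosing day.

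**5. Between arms, worst case.** Assume 30% v 20% withdrawal in 100 patients per arm, g = 0 throughout, and withdrawal on average halfway through 364 days.
- Days lost: 30 × 28 = 840 v 20 × 28 = 560.
- Days observed: 70 × 364 + 30 × 182 = 30,940 v 80 × 364 + 20 × 182 = 32,760.
- Ratio: 840/30,940 = 2.7% v 560/32,760 = 1.7%, a gap of about 1 percentage point.

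**The case against.** The strongest reply is that one sentence of section 4.3 should not be read as the rule. The same section asks for an evaluation when the patient withdraws and for observations up to that time. The early termination column of Table 2 has no study drug. A patient found to have a flare or toxicity at a scheduled visit, and withdrawn before dosing, has been observed for the whole preceding interval. A patient who leaves between visits cannot be evaluated retrospectively on the last dosing day. All of this stands, and it makes zero days a worst case. It does not supply a minimum.

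Four stronger readings are tempting, and the documents do not support them.
- *The last dosing interval goes unobserved in withdrawals.* This is true only at g = 0; the range is 0 to about 28 days.
- *Only the event that caused withdrawal is followed.* Sections 3.11.4 and 7.1.2 follow every ongoing event. The gap is confined to new onsets.
- *Most withdrawals are for flare or toxicity, so the gap falls where harm is likeliest.* The rules in section 3.6 make this plausible, but the protocol gives no figure. Patients also leave for withdrawn consent, noncompliance, pregnancy or changes in background medication.
- *The final antibody sample comes too early to reflect the last dose.* This again needs the zero-day reading, and a positive final result is retested every 8 weeks. Only a patient who is negative at an early final visit would be affected.

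The choice of an on-treatment window for summary tables can also fairly be left to the analysis plan. The collection of the data cannot.

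**Conclusion.** The point holds as a gap in data collection together with timing statements that disagree. Completers are observed for about 28 days after the last dose. Withdrawals are observed for 0 to about 28 days, with no minimum and with a follow-up period of unstated length. What can be lost is limited to new non-serious events and unrelated serious events starting after an early final assessment.

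The size is modest. At most 560 to 1680 patient-days are lost across the trial, assuming 10% to 30% of 200 patients withdraw and every one is assessed on a dosing day; with a 14-day gap the loss is half that. The share is large for an individual only when very few doses were given. A reader might infer that one arm will look safer. That would need withdrawal to differ by arm, and even the worst case worked above differs by only about 1 percentage point of observed time. The primary efficacy analysis is not touched, because section 10.6.3.1 counts withdrawals as nonresponders. This is a cheap improvement to the safety data, not a threat to the trial's main conclusion.

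**What to change.** - Reconcile sections 3.1 (with the note to Figure 1), 3.11.4 and 4.3 so that one time is given for the final assessment of a patient who withdraws.
- In section 7.1.2, define the adverse event period for every dosed patient as consent through the later of the final assessment and 28 days after the last dose. Give the follow-up period mentioned in sections 7.1.2 and 7.1.5.2 the same length.
- In sections 3.11.4 and 4.3, add a telephone safety contact about 4 weeks after the last dose for patients who stop early.

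This gives withdrawals the window that completers already have, and it changes no dose, stopping or treatment rule. The cost is a wording change and one call per early withdrawal: 20 to 60 calls under the withdrawal rates assumed above. Some patients who withdraw consent will not be reachable, so the gap would shrink but not close entirely.

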## 4 SELECTION AND WITHDRAWAL OF PATIENTS

### 4.1 Patient Inclusion Criteria

Patients are included in the study if all of the following criteria are met:

- (a) The patient is a man or woman between 18 and 70 years of age with an established diagnosis of SLE as defined by ACR Classification Revised Criteria. The diagnosis is fulfilled provided that at least 4 criteria are met.
- (b) The patient has a positive test result for ANA at screening (titer must be at least 1:80 [by human epithelial cell tumor line (HEp-2) ANA assay]) **and/or** a positive test result for anti-dsDNA Ab at screening (value must be 30 IU/mL or more by enzyme-linked immunosorbent assay [ELISA]).
- (c) Written informed consent is obtained.
- (d) Women must be surgically sterile, 2 years postmenopausal, or, if of childbearing potential, using a medically accepted method of contraception, and must agree to continued use of this method for the duration of the study and for 30 days after discontinuation of study drug treatment. Acceptable methods of contraception include barrier method with spermicide, abstinence (when this is in line with the preferred and usual lifestyle of the subject), intrauterine device (IUD), or steroidal contraceptive (oral, transdermal, implanted, and injected) in conjunction with a barrier method.
- (e) The patient has a SLEDAI-2K clinical score of at least 6 points **during screening**. A SLEDAI-2K clinical score is the calculated score without inclusion of the points that may be contributed by having a positive titer for anti-dsDNA Ab or decreased serum complement levels.
- (f) The patient does not have an “A” score on the BILAG-2004 scale.
- (g) If the patient is using oral corticosteroids, the weekly cumulative dose must not exceed 80 mg of prednisone equivalent; the weekly dose must be stable over the 4 weeks preceding the 1st dose of study drug.
- (h) If the patient is using antimalarials, methotrexate, leflunomide, MMF, or azathioprine, the start date must be at least 3 months prior to the 1st dose of study drug, and the daily dose

must be stable over the 4 weeks preceding the 1st dose of study drug.

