### **(c) Other Tests**

Other clinical laboratory tests will be performed to ensure the safety of the patients, but will not be an assessment of the safety of the study drug.

At screening (visit 1), patients will have serology A tests for HBsAg and HCV Ab. A urine pregnancy test will be performed for all women, regardless of childbearing potential, at screening (visit 1), baseline (visit 2 [week 0]), visits 4 through 15 (weeks 4 through 48), and the final assessment (or early termination) (visit 16 [week 52]). Any patient becoming pregnant during the study will be withdrawn. All pregnancies that occur during the study, or within 14 days of completion of the study, are to be reported immediately to the individual identified in the clinical study personnel contact information section of this protocol, and the investigator must provide ImmuPharma or its designee, by facsimile, with a signed pregnancy tracking form. The facsimile to the sponsor is to be addressed as follows: to be determined. All patients who become pregnant will be monitored to the completion or termination of the pregnancy. If the pregnancy continues to term, the outcome (health of the infant up to 8 weeks of age) will be reported to the sponsor. Any complication of pregnancy will be reported as an adverse event or serious adverse event, as appropriate.

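### Adverse event recording ends at the final assessment, which is about 4 weeks after the last dose for completers but has no minimum post-dose interval for withdrawn patients

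*Protocol*

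**What the plan says.** Section 7.1.2 fixes the recording window for everyone: "the study period is defined as that time period from signature of the informed consent form through the end of the final assessment". Within it the duty is complete: "All adverse events that occur during the study period must be recorded on the CRF".

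Where that window ends relative to treatment depends on how the patient leaves the study.

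- Completers (3.5): "Patients will return to the study center approximately 4 weeks after administration of the last dose of study drug", that is, at week 52 after a last dose at week 48.
- Withdrawn patients, section 4.3: a full final evaluation when the patient withdraws, with every evaluation to be done "on the last day the patient receives study drug, or as soon as possible thereafter".
- Withdrawn patients, sections 3.1 and 3.11.4 and footnote a of Table 2: at the last visit.
- Withdrawn patients, footnote to Figure 1: at an early termination visit.

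Section 7.1.5.2 asks for serious events to be reported regardless of relationship during the study period, including a follow-up period that it treats as defined elsewhere in the protocol. No such period is set out for withdrawn patients. The only later contact described is repeat antibody testing in patients who are antibody-positive at their final visit (3.1, 3.11.4). After the window closes, 7.1.2 and 7.1.5.2 keep only related serious events reportable.

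On pregnancy, 7.2.4(c) covers "All pregnancies that occur during the study, or within 14 days of completion of the study", while inclusion criterion (d) in 4.1 requires contraception "for 30 days after discontinuation of study drug treatment".

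**The concern.** Two patients who received the same last dose can be watched for different lengths of time after it, depending on whether they completed or withdrew. What can be lost is specific: new non-serious events, and serious events the investigator judges unrelated, that start after an early final visit.

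Withdrawal here is not incidental. Section 3.6 makes it mandatory for a related grade 3 event, any grade 4 event, severe flare, serious intercurrent illness and treatment failure. Ascertainment is therefore least assured in patients with toxicity or active disease. Section 10.7.3 summarises adverse events as patient counts and percentages. If withdrawal differs between arms, unequal observation carries straight into those percentages. An exposure-adjusted rate could allow for unequal time, but it could not recover events that were never collected.

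**Working it through.** **1. The plan's own interval.** Doses are given every 4 weeks from week 0 to week 48: 48/4 + 1 = 13 doses, as sections 3.4.1 and 3.4.2 state. The final assessment is at week 52, and 52 − 48 = 4 weeks. The stated interval for completers is reproduced.

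**2. The interval for a withdrawn patient.** Section 5.1 places dosing after all assessments at a visit, which gives three cases.

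- Final assessment on a dosing day, with the dose given: it precedes that dose, so observation after the last dose is 0 weeks.
- Withdrawal between visits, assessed promptly: between 0 and 4 weeks.
- Withdrawal at the next scheduled visit, with no dose given: about 4 weeks, as for completers.

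The range is 0 to about 4 weeks. If events were spread evenly over the 28 days after a dose (an assumption), the share recorded would be 0%, 25%, 50%, 75% or 100% for a gap of 0, 1, 2, 3 or 4 weeks.

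**3. Upper bound on lost observation.** Planned N is about 200 (3.10). The protocol gives no withdrawal rate or timing, so I assume 10%, 20% or 30% withdrawal with the last dose at week 12, 24 or 36.

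Lost patient-weeks = number withdrawn × (4 − gap in weeks).

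- Gap 0: 20 × 4 = 80; 40 × 4 = 160; 60 × 4 = 240.
- Gap 2: 40, 80 and 120.
- Gap 4: 0.

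**4. As a share of safety time.** Had everyone been observed to 4 weeks after the last dose, total time would be (200 − number withdrawn) × 52 + number withdrawn × (t + 4), where t is the week of the last dose.

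- Smallest share with gap 0 (10% withdrawn, t = 36): 180 × 52 + 20 × 40 = 10,160; 80/10,160 = 0.8%.
- Largest (30% withdrawn, t = 12): 140 × 52 + 60 × 16 = 8,240; 240/8,240 = 2.9%.
- Within the withdrawn patients' own time: 4/40 = 10% (t = 36) to 4/16 = 25% (t = 12).

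**5. Pregnancy window.** For a completer, reporting runs to 28 + 14 = 42 days after the last dose, past the 30 days in 4.1(d). For a withdrawn woman whose final visit is g days after the last dose, and if that visit counts as completion of the study, it runs to day g + 14. That is short of day 30 when g is under 16, and by 30 − 14 = 16 days when g = 0. Section 3.11.4, however, reserves completion for patients treated for at least 48 weeks, so it is unclear how the rule applies to her at all.

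**The case against.** The strongest reply is that the visit structure makes a zero gap unusual. Because assessments come before dosing, a flare, toxicity or prohibited treatment found at a scheduled visit can lead to withdrawal then, with no further dose, and the final assessment falls about 4 weeks after the previous one. Often nobody knows at the time that a dose will be the last, so only the second half of the rule in 4.3 can operate. This stands. A reader might infer from 4.3 that withdrawn patients are always assessed on their last dosing day. The text does not support that, and the other sections describe the timing differently.

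The existing safeguards also count. Related serious events remain reportable without a time limit. Adverse events already recorded, and those that caused withdrawal, are followed until they settle, pass to local care or are found to have another cause (4.3, 7.1.2, 7.1.6). So it would be wrong to conclude that post-dose events in general are missed. These provisions do not, however, reach new non-serious or unrelated serious events.

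Finally, bias is not shown. It needs withdrawal to differ by arm and events to fall in the unobserved interval, and the protocol plans only descriptive safety summaries. That makes the distortion a possibility rather than a result. It does not remove the unequal ascertainment.

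**Conclusion.** The point holds in limited form. The protocol sets no minimum post-dose recording interval for withdrawn patients, describes their final assessment in several ways that do not agree, and refers to a follow-up period that it does not define for them. Followed as written, it leaves some new non-serious events and unrelated serious events uncollected.

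The loss is at most 80 to 240 patient-weeks, or 0.8% to 2.9% of all safety time, and 10% to 25% of the withdrawn patients' own time. These are ceilings: they assume 10% to 30% withdrawal, last doses at weeks 12 to 36, and no post-dose observation in any withdrawn patient. The actual loss may be near zero. Overall adverse event rates would hardly move; the weakness lies in the patients who stop early, and a distorted arm comparison would require differential withdrawal.

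The pregnancy point is secondary. A reader might infer a fixed 16-day shortfall, but that needs both a final visit on the last dosing day and a particular reading of study completion. What the documents do show is that the window is unclear for withdrawn women and could end before the contraception period does.

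**What to change.** Reconcile sections 3.1 (with the Figure 1 footnote), 3.11.4, 4.3, 7.1.2 and 7.1.5.2 so that they give one timing for the final assessment after withdrawal and define the follow-up period. In 7.1.2, have adverse event recording for every patient run to the same interval after the last dose that completers already have, about 4 weeks. When the final visit comes earlier, add one telephone adverse event inquiry at that point.

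Reconcile 7.2.4(c) with 4.1(d) by stating the pregnancy reporting window relative to the last dose, so that its application to withdrawn women is plain.

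The cost is amendment wording and one call per early-withdrawn patient: about 20 to 60 calls at the assumed 10% to 30% withdrawal. No extra site visit is needed, and dosing and clinical management are unchanged.
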